## **10.0 Statistical Considerations**

### **10.1 Power Analysis and Sample Size Calculation**

#### **D.3.c. Sample size calculation for Aims 1 and 2.**

$\beta$ -cell function, glucagon suppression, and IL-33 signaling are the primary outcomes for the aims. Sample size was calculated using a 2-group t-test with PS Software (version 3.0, Dupont&Plummer, 2009) at a 0.05 two-sided significance level. We estimate a 50% incidence of PTDM by day+100 (1, 8, 14). The sample size provides at least 80% power to detect a biologically meaningful difference in mean between patients with and without PTDM for each aim. The same patient cohort will be monitored for all aims. We will enroll 34 patients to ensure at least 80% power for each aim. Assuming the dropout rate is about 10% (early death or pre-HCT diagnosis of diabetes by OGTT), an additional 6 subjects will be recruited (41-43). Forty subjects are feasible to accrue over 4 years, given that 151 patients underwent allogeneic HCT at Vanderbilt in 2015.

**Subaim 1A primary outcome: second-phase GSIS.** A mean difference of 7.5  $\mu$ U/mL represents a significant difference in second-phase insulin release between healthy controls and individuals at risk for type 2 diabetes (44-46). A sample size of 17 patients in each group (either with or without PTDM) has 80% power to detect at least a 7.5  $\mu$ U/mL difference in insulin secretion between groups using a standard deviation of 7.5  $\mu$ U/mL.

**Subaim 1B primary outcome: glucagon secretion during OGTT.** AUC was calculated for each patient to present as total glucagon secretion during OGTT. Our preliminary data observed  $8.83 \pm 0.73$  pg/mL•min (mean  $\pm$  SD) in log(AUC) scale for patients with PTDM (Figure 4). With a sample size of 9 each group, there is 80% power to detect a log(AUC) change of from 8.83 pg/mL•min to 7.83 pg/mL•min.

**Aim 2 primary outcome: IL-33 signaling** Extrapolating our preliminary and pre-clinical data, a mean difference of 70 pg/mL is likely to represent a significant difference in IL-33 signaling between groups (14, 20). With a sample size of 17 in each group, there is 80% power to detect a 70 pg/mL difference in IL-33 production between groups using a standard deviation of about 70 pg/ml.

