### *Secondary analyses for Subaims 1A and 1B*

1) determining if glucagon secretion and OGTT results pre-transplant predict PTDM development (herein OGTT results refers to 2 hour blood glucose and peak/nadir/total hormone levels during OGTT), 2) determining if GLP-1 infusion increases insulin secretion and glucagon suppression compared to OGTT values without GLP-1, 3) comparing GSIS, glucagon suppression, and OGTT results at day +90 among patients with or without established PTDM, and 4) comparing the change in GSIS, glucagon suppression, and OGTT results at baseline to those determined at day +90 after transplant in the entire cohort or among groups stratified based on PTDM, conditioning regimen (ablative vs. reduced intensity) or for the presence or absence of acute GVHD treated with steroids.

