### *Secondary analyses for Aim 2*

1) determining if PTDM is predicted by pre- or post-transplant levels of IL-33/sST2 from serum/tissue microdialysate, or by the frequency of circulating ST2+Th1 cells and ST2+Tregs, 2) analyzing whether IL-33/sST2 levels and ST2+Th1 cells and ST2+Tregs correlate with insulin/glucagon secretion during OGTT and hyperglycemic clamps, 3) test whether *in vitro* exposure of HCT recipient CD4+ T cells to IL-33 promotes proliferation and inflammatory Th1 immunity, and 4) test if *in vitro* exposure of human islets to IL-33 impairs insulin secretion and decreases islet cell viability in culture.

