### *General statistical plan*

Data will be presented using means and standard deviations for continuous variables, as well as percentage and frequency for categorical variables. Investigations for outliers and assumptions for statistical analysis, e.g., normality and homoscedasticity will be made for the parametric test such as t-test and mixed model. If necessary, data will be transformed utilizing appropriate transformations such as the log or square root. Comparison between two independent groups, e.g., with or without PTDM, will be carried out using either two-sample t-test or Wilcoxon rank sum test for continuous variables and Chi-square test or Fisher's exact test for categorical variables. A Spearman correlation will be used to test the relationship between 2 continuous variables. For matched analyses and for the comparison of the changes between baseline and day+90 after transplant in the entire cohort, the mean difference will be compared with paired Student's t-test or Wilcoxon signed rank test for continuous

variables and a McNemar's test for categorical variables. To compare the differences between baseline (pre-transplant) and day +90 test results among various groups we will apply linear mixed model to continuous outcomes and generalized linear mixed model to binary/ordinal outcomes. Groups of interest will be created by stratifying patients based on PTDM, conditioning regimen (ablative vs. reduced intensity) or acute GVHD treated with steroids. All data will be stored in a computerized database and analyzed with R version 3.3.1 (R Foundation for Statistical Computing, Vienna, Austria). *P*-values will be 2-tailed and considered significant at *P* <0.05.

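### The plan calls any secondary result with P<0.05 significant, with no multiplicity control or exploratory label, although its secondary lists imply roughly 75 to 330 tests

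*Combined protocol and SAP*

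**What the plan says.** The General statistical plan in Section 10.2 ends with a rule that covers every analysis: P "values will be 2-tailed and considered significant at" the 0.05 level. Section 10.1 uses the same level for sample size ("at a 0.05 two-sided significance level") and names one primary outcome each for Subaim 1A (second-phase GSIS), Subaim 1B (glucagon secretion during the OGTT) and Aim 2 (IL-33 signaling).

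Section 10.2 then gives two lists of secondary analyses, with four items each. For Subaims 1A and 1B, OGTT results are defined as the 2-hour glucose plus peak, nadir and total hormone levels. The fourth item is "comparing the change in GSIS, glucagon suppression, and OGTT results at baseline to those determined at day +90" after transplant, in the whole cohort or by PTDM, conditioning regimen or steroid-treated acute GVHD. For Aim 2, the first item asks whether several markers in serum, microdialysate and circulating cells predict PTDM. The second is "analyzing whether IL-33/sST2 levels and ST2+Th1 cells and ST2+Tregs correlate with insulin/glucagon secretion during OGTT and hyperglycemic clamps". The last two are in vitro experiments.

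Sections 10.1 and 10.2 contain no multiplicity adjustment, testing order, key secondary outcome or false-discovery control, and they do not call the secondary analyses exploratory.

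**The concern.** A single unadjusted threshold gives each secondary comparison the same route to the word *significant* as a primary outcome. With long crossed lists and about 17 patients per group, some comparisons will pass the threshold by chance, and a reader of the results would have no stated way to tell these from real signals. This matters because the Rationale and clinical application part of Section 2.0 expects the OGTT and clamp results to feed later screening tools and therapeutic trials. A chance finding presented as an established islet or immune mechanism could misdirect that work.

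**Working it through.** **The plan's own figure.** Section 10.1 states: "A sample size of 17 patients in each group (either with or without PTDM) has 80% power to detect at least a 7.5" µU/mL "difference in insulin secretion between groups using a standard deviation of 7.5" µU/mL. The standardised difference is 7.5/7.5 = 1.0. A two-sample t-test at two-sided 0.05 needs 16.7, so 17 per group, and has 80.7% power at 17. Aim 2 (70 pg/mL, SD about 70) is the same calculation. The figure reproduces. It is based on one test at 0.05 and makes no allowance for other tests.

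**Inputs for the count.**
- OGTT analytes (Section 6.0, OGTT): glucose and four hormones (insulin, glucagon, C-peptide, GLP-1). If peak, nadir and total are taken for all four hormones, there are 1 + 3 × 4 = 13 OGTT measures.
- Clamp measures (Section 6.0, Calculations): two GSIS phases, each with two formulas, repeated for C-peptide and glucagon, plus three arginine responses. The smallest set used here is two insulin phases and one glucagon-suppression measure, so 3.
- Comparisons of change: up to four (whole cohort, PTDM, conditioning, treated GVHD).
- Blood draws: five. Microdialysis: two occasions.

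**Middle reading** (all 13 OGTT measures, all draws, one GSIS formula, insulin GSIS only):
- Aim 1, item 1: 13
- Aim 1, item 2, insulin and glucagon at two times: 2 × 2 = 4
- Aim 1, item 3: 13 + 3 = 16
- Aim 1, item 4: 16 × 4 = 64
- Aim 2, item 1, four blood markers at five draws plus two microdialysate markers at two times: 20 + 4 = 24
- Aim 2, item 2, four markers × two hormones × two procedures × two times: 32

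Total: 13 + 4 + 16 + 64 + 24 + 32 = 153.

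**Other readings**, items in the same order:

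| Reading | Items | Total | Total × 0.05 |
|---|---|---|---|
| Lean: 2-hour glucose and hormone totals only (5 OGTT measures); one pre- and one post-transplant value per marker; item 2 and correlations at one time | 5 + 2 + 8 + 32 + 12 + 16 | 75 | 3.75 |
| As lean, but with 9 OGTT measures (peak and total for three hormones, nadir and total for glucagon) | 9 + 2 + 12 + 48 + 12 + 16 | 99 | 4.95 |
| Middle | as above | 153 | 7.65 |
| Full: both OGTTs (26 measures); 12 GSIS-type clamp measures and 3 arginine responses; two summary measures per correlation | 26 + 4 + 41 + 164 + 24 + 64 | 323 | 16.15 |

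Four in vitro tests (T-cell proliferation, Th1 response, islet insulin secretion, islet viability) would raise these totals to 79, 103, 157 and 327.

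**Overlap with the primary outcomes.** The middle count includes day +90 OGTT glucagon total by PTDM, which is the Subaim 1B primary comparison, and serum IL-33 by PTDM, which is the Aim 2 primary comparison. Removing one test for each leaves 151. Removing all five IL-33 draws leaves 147. The expectation is then 147 × 0.05 = 7.35 to 151 × 0.05 = 7.55, so little changes.

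**Expected false positives.** For m tests with every null true, the expected number below 0.05 is m × 0.05, whatever the correlation between tests. Correlation affects only how the errors cluster. The range is about 4 to 16.

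**The case against.** The strongest reply is that this is an observational, mechanistic study with one named primary outcome per aim or subaim, and that the other analyses are already headed as secondary. Much of that stands. The headings do rank the analyses, and the primary comparisons do not depend on how the secondary ones are labelled. But a heading does not override a rule that calls every P below 0.05 significant, and the plan nowhere says that the secondary analyses generate hypotheses only.

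The count can also be challenged. The list offers the whole cohort *or* stratified groups, so item 4 need not be run four ways on every measure. Nadir may be meant for glucagon only. No time points are given for the correlations. These objections are sound, and they are why a range is given. A reader might infer that the plan commits the study to at least 150 tests and therefore to seven or eight false findings. The documents do not support this: 150 is a middle reading and not a floor, and the leaner readings give 75 to 99 tests, with 4 to 5 expected.

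Nor are all the nulls plausible. PTDM is defined by glucose, so a null for day +90 2-hour glucose by PTDM status is unlikely. Section 3.0 already describes GLP-1 as promoting insulin release and glucagon suppression. Related measures, such as peak and total of one hormone, will also give clustered errors. All of this stands and limits what the expected number means.

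A reader might also infer that unadjusted secondary P-values will be carried straight into screening tools. Section 2.0 speaks of the OGTT and clamp results in general and does not say so.

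**Conclusion.** The point holds as a gap in the reporting rule. As written, the plan would call any secondary result with P<0.05 significant, with no error-rate control and no exploratory label. Between about 75 and 330 tests are implied, so about 4 to 16 false-positive results would be expected if all nulls were true. The count is this review's reading of the lists and is not a figure in the documents. The expectation is a complete-null benchmark, and the real number of false positives will be lower to the extent that some effects exist.

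The number of patients is not fixed across these tests. The plan needs 34 and recruits 40. A figure of 36 (40 × 0.9) is only derived, patients with diabetes on the pre-transplant OGTT remain in the Aim 2 immune studies, and the islet experiments use cadaver-donor tissue.

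The design, the sample size and the primary comparisons are not called into question by this point.

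**What to change.** Replace the closing rule of the General statistical plan with wording such as:

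> P<0.05 is used to declare significance only for the primary outcome of each aim or subaim (second-phase GSIS, post-transplant OGTT glucagon AUC, serum IL-33). All secondary analyses are exploratory, are reported with estimates and 95% CIs, are not described as significant on an unadjusted P<0.05, and all tests performed are listed.

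First-phase GSIS, which Section 10.2 includes in the primary analysis of Subaim 1A but Section 10.1 does not name as a primary outcome, would then fall under the exploratory rule.

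Benjamini-Hochberg adjusted P-values within an Aim 1 and an Aim 2 family may be added as an option. They should not be required: the families would have to be enumerated in advance, and the power cost is real. With the 97 Aim 1 tests of the middle reading (13 + 4 + 16 + 64) and a 10% false-discovery rate, the first threshold is 0.10/97 = 0.001. For a 1-SD difference with 18 per group, power at that threshold is about 30%, against 83% at 0.05.

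The recommended change needs only plan wording and a record of the tests run. Its downside is that fewer secondary results can be called significant.

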## **11.0 Privacy/Confidentiality Issues**

A unique alphanumeric code will be assigned to each study participant to protect their confidentiality. Clinical information and laboratory data will be kept in a password protected database maintained by and accessible to the study investigators and research staff. The key to decode patient identity will be kept in a password protected database. Only the investigators and research staff will have access to the database. All communications with non-investigators of this study and any publication of results will identify patients by code only to protect patient identity.

## **12.0 Followup and Record Retention**

All research records including study results will be retained for at least 6 years after the study is finished. At that time, the research data that has not been put in a participant's medical record and all study samples will be kept for an unknown length of time. Any research data that has been put into a participant's medical record will be kept for an unknown length of time.

## Appendix A

### Study Table - Donor

	Baseline	Pre-Collection
Study Blood collection		X
Informed Consent	X	
Review of Eligibility	X	
Data Collection	X	X

Study Table - Patient

	Baseline	Pre-Transplant	Day 10 post-transplant	Day 20 post-transplant	Day 30 post-transplant	Day 80-100 post-transplant	D365 post-transplant	D730 post-transplant
Study Blood collection	X		X	X	X	X		
OGTT / Microdialysis - CRC visit		X				X		
OGTT / GLP-1 Infusion - CRC visit		X				X		
Hyperglycemic Clamp - CRC visit		X				X		
Informed Consent	X							
Review of Eligibility	X							
Data Collection	X	X	X	X	X	X	X	X

All dates for blood collection +/- 7 days, all dates for procedures / study visits +/- 10 days

Oral glucose tolerance testing and the hyperglycemic clamps will be performed on separate days as scheduling allows
